4.1.3 Medical history date of diagnosis imputation

Medical history date of diagnosis imputation for the Core study

Completely missing dates and partially missing diagnosis dates will not be imputed. Partial dates of diagnosis will be compared to the treatment start date.

- If DIAG year <= Core study treatment start date year and DIAG month is missing, the imputed DIAG date is set to the mid-year point (01JULYYYY)
 - else if DIAG month is not missing, the imputed DIAG date is set to the mid-month point (15MONYYYY)
- If DIAG year = Core study treatment start date year
 - and (DIAG month is missing OR DIAG month is equal to Core study treatment start month), the imputed DIAG date is set to one day before Core study treatment start date
 - else if DIAG month <= Core study treatment start month, the imputed DIAG date is set to the mid-month point (15MON YYYY)
 - else if DIAG month > Core study treatment start month => data error
- If DIAG year > Core study treatment start date year => data error

Medical history diagnose year imputation for the Extension study

Completely missing dates and partially missing end dates will not be imputed. Partial dates of diagnosis will be compared to the end of Core study date (if medical conditions is ongoing at the end of Core study but not ongoing at Extension baseline) , the ExtensionICF signsignsign date (if medical conditions is ongoing at Extension baseline), .

If medical condition is ongoing at the end of Core study but not ongoing at Extension baseline:

Completely missing dates and partially missing end dates will not be imputed. Partial dates of diagnosis will be compared to end of Core study date.

- If diagnosis year <= end of Core study date year and diagnosis month is missing, the imputed diagnosis date is set to the mid-year point (01JULYYYY)
 - else if diagnosis month is not missing, the imputed diagnosis date is set to the mid-month point (15MONYYYY)
- If diagnosis year = end of Core study date year
 - and (diagnosis month is missing OR diagnosis month is equal to end of Core study date month), the imputed diagnosis date is set to one day before end of Core study date
 - else if diagnosis month < end of Core study date month, the imputed diagnosis date is set to the mid-month point (15MON YYYY)
 - else if diagnosis month > end of Core study date month => data error
- If diagnosis year > end of Core study date year => data error

If medical condition is ongoing at Extension baseline (CIF sign date):

- If diagnosis year <= Extension ICF sign date year and diagnosis month is missing, the imputed diagnosis date is set to the earlier of (mid-year point (01JULYYYY), Extension ICF sign date ---1)
 - else if diagnosis month is not missing and not equal to ICF sign date month, the imputed diagnosis date is set to the earlier of (mid-month point (15MONYYYY), Extension ICF sign date---1)
 - else if diagnosis month equal to Extension ICF sign date month, the imputed diagnosis date is set to one day before Extension ICF sign date
 - ICF > Extension ICF sign date month => data error
- If diagnosis year > Extension ICF sign date year => data error

4.1.4 Concomitant treatment date imputation

Concomitant treatment end date imputation

If the concomitant treatment end date year value is missing, the date uncertainty is too high to impute a reliable date. Therefore, if the concomitant treatment end year value is missing or ongoing, the imputed concomitant treatment end date is set to NULL.

Else, if the concomitant treatment end date month is missing, the imputed end date should be set to the earliest of the (treatment follow up period date, 31DECYYYY, date of death).

If the concomitant treatment end date day is missing, the imputed end date should be set to the earliest of the (treatment follow up period date, last day of the month, date of death).

If the imputed concomitant treatment end date is before the existing concomitant treatment start date, use the concomitant treatment start date as the imputed concomitant treatment end date.

Concomitant treatment start date imputation

In order to classify a medication as prior and prior/concomitant, it may be necessary to impute the start date.

If medication is ongoing at the last visit of Core study:

Completely missing start dates will be set to one day prior to start treatment date.... Concomitant treatments with partial start dates will have the date or dates imputed. Partial concomitant treatment start dates are imputed with reference to the treatment start date (TRTM) in accordance with the rules outlined below:

	Day	Month	Year
Partial CMD Start Date	Not used	MON	YYYY
Treatment Start Date (TRTM)	Not used	TRTM	TRTY

The following matrix explains the logic behind the imputation.

	MON MISSING	MON < TRTM	MON = TRTM	MON > TRTM
YYYY MISSING	Uncertain	Uncertain	Uncertain	Uncertain
YYYY < TRTY	01JULYYYY Before treatment start	15MONYYYY Before treatment start	15MONYYYY Before treatment start	15MONYYYY Before treatment start
YYYY = TRTY	Uncertain	15MONYYYY Before treatment start	Uncertain	01MONYYYY After treatment start
YYYY > TRTY	01JANYYYY After treatment start	01MONYYYY After treatment start	01MONYYYY After treatment start	01MONYYYY After treatment start

If medication is not ongoing at the last visit of Core study:

Completely missing start dates will be set to one day prior to Extension baseline visit date. Concomitant treatments with partial start dates will have the date or dates imputed. Partial concomitant treatment start dates are imputed with reference to the Extension baseline visit date (EXTBL) in accordance with the rules outlined below:

	Day	Month	Year
Partial CMD Start Date	Not used	MON	YYYY
Extension Baseline Visit Date (EXTBL)	Not used	TRTM	TRTY

The following matrix explains the logic behind the imputation.

	MON MISSING	MON < EXTL	MON = EXTL	MON > EXTL
YYYY MISSING	Uncertain	Uncertain	Uncertain	Uncertain
YYYY < EXTL	Later of (01JULYYYY, date of last visit of Core study +1) Before Extension baseline visit	Later of (15MONYYYY, date of last visit of Core study +1) Before Extension baseline visit	Later of (15MONYYYY, date of last visit of Core study +1) Before Extension baseline visit	Later of (15MONYYYY, date of last visit of Core study +1) Before Extension baseline visit

YYYY = EXTBL	Uncertain	Later of (15MONYYYY, date of last visit of Core study +1) Before Extension baseline visit	Uncertain	01MONYYYY After Extension baseline visit
YYYY > EXTBL	01JANYYYY After Extension baseline visit	01MONYYYY After Extension baseline visit	01MONYYYY After Extension baseline visit	01MONYYYY After Extension baseline visit

The following table is the legend to the logic matrix.

Relationship	
Before Extension baseline visit	Partial date indicates CMD start date prior to Extension baseline visit Date
After Extension baseline visit	Partial date indicates CMD start date after Extension baseline visit date
Uncertain	Partial date insufficient to determine relationship of CMD start date to Extension baseline visit date

If a complete (imputed) CM end date is available and the imputed CM start date is greater than the (imputed) CM end date, then the imputed CM start date should be set to the (imputed) CM end date.

4.2 Laboratory parameters derivations

Not applicable.

4.3 Statistical models and SAS codes

CMH test:

The primary efficacy variable is the visual acuity (VA) in the better-seeing eye at the patient's fifth birthday as recorded by the investigator.

The following primary hypothesis will be used to test the comparison of ranibizumab 0.2 mg versus laser as follows:

$$H_{01}: \mu_{\text{ranibizumab 0.2 mg}} - \mu_{\text{Laser}} = 0 \text{ versus } H_{A1}: \mu_{\text{ranibizumab 0.2 mg}} - \mu_{\text{Laser}} \neq 0$$

where $\mu_{\text{Treatment}}$ arm is the unknown mean VA in the better-seeing eye at the fifth birthday of patients in the relevant treatment arm.

The hypothesis will be tested by using stratified analysis of variance (ANOVA) using the Cochran-Mantel-Haenszel (CMH) test with the observed VA values as the response variable and the treatment arm as the factor (with levels 0.2 mg and laser). Stratification will be based on the ROP zone at the Core study baseline.

The test statistics can be written in the form (Lehmann, E. L. (1975) and Van Elteren, P.H. (1960)):

$$W^* = \frac{\sum_{j=1}^J a_j \sqrt{\frac{n_{0j}n_{1j}}{n_{0j} + n_{1j}}} \left(\frac{1}{n_{0j}} \sum_{k=1}^{n_{0j}} R_{0jk} - \frac{1}{n_{1j}} \sum_{k=1}^{n_{1j}} R_{1jk} \right)}{\sqrt{\sum_{j=1}^J a_j^2 \frac{1}{n_{0j} + n_{1j} - 1} \sum_{i=0}^1 \sum_{k=1}^{n_{ij}} (R_{ijk} - \bar{R}_{\bullet,j})^2}}$$

where R_{ijk} is the VA sCore of subject k within strata j of treatment i , $i=0,1$ denotes the treatment arm, $j=1, 2$ denotes the ROP zone, $k=1, \dots, n_{ij}$ denotes the subjects within the i^{th} treatment arm in the j^{th} ROP zone and $\bar{R}_{\bullet,j}$ is the average VA sCore of all subjects in Zone j .

For large sample sizes (within each strata) the test statistic has a standard normal distribution; therefore the two-sided test would reject the null hypothesis if $|W^*| > Z_{\alpha/2}$, where Z is the $N(0, 1)$ distribution.

The option CMH with SCORESSCORES=TABLE in the OUTPUT statement requests the CMH row means sCore statistics and the corresponding two-sided p-value:

```
proc freq data = <input_dataset sorted> noprint;
tables <stratavar> * <treatmentvar> * <responsevar> / CMH
SCORESSCORES=TABLE ;
output out = <output_dataset> (keep = _CMHRMS_ P_CMHRMS) CMH;
run;
```

The two-sided p-value will then be converted to a one-sided p-value: For each comparison, if the direction of the observed difference supports the superiority outcome (e.g. mean difference > 0), the two-sided p-value will be converted to a one-sided p-value by dividing by two. If mean difference < 0 , the one-sided p-value will be calculated as 1 - (the two-sided p-value divided by two).

ANOVA model:

The ANOVA analysis will be performed using SAS procedure PROC MIXED.

Stratified ANOVA:

```
proc mixed data = <input_dataset sorted> noprint;
class <treatmentvar> <stratavar>;
model <responsevar> = <stratavar> <treatmentvar> ;
lsmeans <treatmentvar> / om;
estimate ""<treatmentvar>;
run;
```

Unstratified ANOVA:

```
proc mixed data = <input_dataset sorted> noprint;
class <treatmentvar>;
model <responsevar> = <treatmentvar> ;
lsmeans <treatmentvar> / om;
estimate ""<treatmentvar>;
run;
```

Calculating 95% confidence intervals for proportions using Clopper-Pearson method:

[figure not shown]
The confidence intervals for the proportions will be calculated using the Clopper-Pearson method. It will be performed using SAS procedure PROC FREQ with the BINOMIAL option in the TABLES and EXACT statements:

[figure not shown]
```
proc freq data = <input_dataset sorted> noprint;  
by <treatmentvar>;  
tables <responsevar> / binomial (cl=exact );  
exact binomial;  
run;
```

[figure not shown]

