2.6.2 Statistical hypothesis, model, and method of analysis

If the primary hypothesis testing in the Core study shows statistical significance, the primary objective is to compare ranibizumab 0.2 mg versus laser with an informal testing as follows:

$$H_{01}: \mu_{\text{ranibizumab 0.2 mg}} - \mu_{\text{Laser}} = 0 \text{ versus } H_{A1}: \mu_{\text{ranibizumab 0.2 mg}} - \mu_{\text{Laser}} \neq 0$$

where $\mu_{\text{Treatment}}$ arm is the unknown mean VA in the better-seeing eye at the fifth birthday of patients in the relevant treatment arm.

The hypothesis will be tested by using stratified analysis of variance (ANOVA) using the Cochran-Mantel-Haenszel (CMH) test with the observed VA values (letters) as the ordinal response variable and the treatment arm as the factor (with levels ranibizumab 0.2 mg and laser). The effect of ROP zone at the baseline of the Core study is expected to have an effect at 5 years of age. Hence this variable is used as stratification factor in the analysis.

If the primary hypothesis testing in the Core study does not show statistical significance, only descriptive statistics (i.e., point estimate, and the 95% confidence interval) will be provided for the comparison between ranibizumab 0.2 mg and laser.

In addition, an unstratified two-way ANOVA using VA as the response variable and treatment arm and ROP zone as factors will be performed. This is essentially a one-way ANOVA using VA as the response variable and treatment arm as the factor, without ROP zone as the stratification factor. Two-sided 95% confidence intervals, assuming normality, will be produced for the VA within each treatment arm and the difference in VA between a pair of treatment arms will be calculated from least squares means. No p-values will be displayed for this analysis.

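### SAP Section 4.3 turns the two-sided CMH p-value for visual acuity into a one-sided one, against the two-sided hypothesis and rejection rule the SAP states

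*SAP*

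**What the plan says.** SAP Section 2.6.2 gives the alternative for ranibizumab 0.2 mg against laser as a difference in means not equal to zero. The test is conditional: "If the primary hypothesis testing in the Core study shows statistical significance", the comparison is tested informally; otherwise only descriptive statistics are given.

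Section 4.3 repeats the not-equal alternative and gives the large-sample rule: "therefore the two-sided test would reject the null hypothesis if" |W*| exceeds Z(alpha/2). It says the PROC FREQ option "requests the CMH row means sCore statistics and the corresponding two-sided p-value".

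The next paragraph of Section 4.3 changes course: "The two-sided p-value will then be converted to a one-sided p-value". For each comparison, the two-sided value is halved "if the direction of the observed difference supports the superiority outcome (e.g. mean difference > 0"). If the mean difference is below zero, "the one-sided p-value will be calculated as 1 - (the two-sided p-value divided by two").

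Section 2.8.1 applies the primary CMH approach to 0.1 mg against laser and 0.2 mg against 0.1 mg for the better-seeing eye, and to all three pairs for the worse-seeing eye. Section 2.6.4 repeats the CMH test if enough patients received a medication that rules out further study treatment.

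The intervals come from a separate ANOVA in Section 2.6.2: "Two-sided 95% confidence intervals, assuming normality, will be produced for the VA within each treatment arm", and likewise for differences between arms. For that ANOVA, "No p-values will be displayed for this analysis".

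**The concern.** The hypothesis, the rejection rule and the software output are all two-sided. The conversion is mandatory in wording, yet the SAP does not say whether the two-sided or the converted value is the one displayed. A programmer cannot satisfy both parts of Section 4.3 with one p-value.

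The direction is also not fixed. It is given through an example (a positive mean difference), which for 0.2 mg minus laser points to ranibizumab, but it appears in no hypothesis. For 0.2 mg against 0.1 mg, no arm is named as the one expected to be superior. A conversion built on a superiority outcome also sits badly with Section 2.1, which says the tests are not meant to support superiority claims.

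At stake is how the visual acuity evidence at the fifth birthday is described. A difference favouring ranibizumab would carry half its two-sided p-value. A clear difference against ranibizumab would carry a p-value close to 1, which reads as no evidence of a difference.

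**Working it through.** The SAP gives no sample size, power or numeric alpha for this test, so it has no figure to reproduce. The check applies the conversion rule of Section 4.3 to that section's large-sample standard normal W*. No sample size is needed.

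**Formulas**
- Two-sided: p = 2 × (1 - Φ(|W*|)).
- Converted, favourable: p/2.
- Converted, unfavourable: 1 - p/2.

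**Results**

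| \|W*\| | Two-sided p | Converted, favourable | Converted, unfavourable |
|---|---|---|---|
| 1.75 | 0.0801 | 0.0401 | 0.9599 |
| 2.00 | 0.0455 | 0.0228 | 0.9772 |
| 2.576 | 0.0100 | 0.0050 | 0.9950 |

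For example, at |W*| = 2.00 the two-sided value is 0.0455. Then 0.0455/2 = 0.0228, and 1 - 0.0228 = 0.9772.

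**What this does to the test.** A cut-off has to be assumed, because the SAP states none.
- Two-sided at 0.05: critical value 1.960, with 2.5% in each tail. This matches the stated alternative and rule.
- Converted value read against 0.05: critical value 1.645, with 5% in the upper tail and nothing in the lower tail. For a favourable difference this equals a two-sided test at 2 × 0.05 = 0.10.
- Converted value read against 0.025: critical value 1.960 on the favourable side, the same as the two-sided 0.05 test. A difference favouring the comparator still cannot register.

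A null simulation of the stratified statistic gave the same picture (20,000 runs; two strata with assumed arm sizes 20/18 and 35/33). At 0.05 the two-sided value rejected in 4.95% of runs and the converted value in 4.9%. None of the converted rejections had a negative W*.

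**Reach, counted from the text**
- Section 2.6.2: 1 comparison, if the Core study condition is met.
- Section 2.8.1: 2 (better-seeing eye) + 3 (worse-seeing eye) = 5. The section does not say whether the Core study condition carries over.
- Section 2.6.4: the CMH repeat, if enough patients qualify. The other supportive analyses there do not name the CMH test and are not counted.

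**The case against.** The contradiction itself is hard to dispute; the case on the other side is that it matters little. Testing is informal, Section 2.1 disclaims significance thresholds, and the primary test runs only if the Core study succeeded. The SAS code keeps the two-sided value, and the conversion can be undone exactly once the sign of the difference is known. No estimate, interval or analysis set changes. All of this stands, and it limits the consequence to reported p-values.

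Three narrower points also have some force:
- The rule 1 - p/2 gives values anywhere from 0.5 to 1, so only clearly unfavourable differences come close to 1.
- Section 2.8.1 mentions point estimates that favour ranibizumab over laser, so the expected direction can be inferred for those pairs. It still cannot for 0.2 mg against 0.1 mg, and no hypothesis states it for any pair.
- The p-values and the intervals come from different models whatever is done about the conversion, and a one-sided p-value does not in itself claim superiority. The difference in model is therefore not caused by this step, and the tension with Section 2.1 is secondary.

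None of this reconciles the two halves of Section 4.3. Undoing the conversion also requires the output to state sidedness and direction, which the SAP does not ask for.

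**Conclusion.** The point holds. Followed as written, Section 4.3 produces p-values that do not test the not-equal alternative of Sections 2.6.2 and 4.3: favourable values are halved, and unfavourable ones are moved above 0.5, close to 1 when the difference is large. The step covers the five visual acuity comparisons of Section 2.8.1 if those tests are run. It also covers the primary comparison and the Section 2.6.4 repeat when their conditions are met.

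The p-values above rest only on the normal form of W* given in the SAP; statements about rejection rest on an assumed 0.05 or 0.025 level. Because testing is informal, no formal decision changes. It should still be fixed, since it affects the reported p-value for the primary endpoint and the correction is simple.

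**What to change.** Delete the conversion paragraph in Section 4.3. For every visual acuity comparison that uses the CMH test, report the two-sided P_CMHRMS with the point estimate, in line with the stated alternative and the |W*| rule.

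If one-sided tests are in fact intended, state one-sided hypotheses and the direction of each comparison, including 0.2 mg against 0.1 mg, consistently in Sections 2.6.2, 2.8.1 and 4.3. The level against which the values are to be read should be given as well.

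The deletion costs one paragraph and needs no new data or analysis. Relative to the converted values, favourable p-values double and unfavourable ones return to their two-sided size.

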4.4 Rule of exclusion criteria of the analysis setset

[figure not shown]
Table 4-1 Protocol deviations that cause subjects to be excluded

Deviation ID	Description of Deviation	Exclusion in Analyses
INCL01	Informed consent was not obtained before study related assessment performed	Excluded from extension safety set: both safety and efficacy analysis
WITH02	Patient was not withdrawn from the study despite withdrawal of consent	Excluded from extension safety set: both safety and efficacy analysis

5 Reference

1. Lehmann, E. L. (1975). Nonparametrics: Statistical Methods Based on Ranks, San Francisco: Holden-Day, pp 132-137, 145.
2. Van Elteren, P. H. (1960). "On the combination of independent two-sample tests of Wilcoxon, Bulletin of the International Statistical Institute", 37, 351-361.
3. Newcombe R.G., Two-sided CIs for the single proportion: comparison of seven methods, *Statistics in Medicine*, (1998) 17, 857-872
4. Newcombe R.G., Interval Estimation for the Difference between Independent Proportions: Comparison of Eleven Methods. *Statistics in Medicine* 1998; 17: 873-890
